#### 6.5.6 Safety Laboratory Tests

All laboratory parameters assessed will be evaluated centrally. However, laboratory tests for safety evaluation, such as hematology, clinical chemistry and coagulation parameters will also be assessed locally at indicated times during each cycle. In exceptional circumstances, the use of local labs may also be considered for assessment of screening laboratory values, after approval by the medical monitor.

Refer to the Schedule of Assessments (Table 6-1, Table 6-2 and Table 6-8) for a summary of the parameters to be evaluated.

More frequent evaluations may be performed at the Investigator's discretion if medically indicated; results should be recorded as unscheduled laboratory assessments.

Laboratory tests will be performed as described below and according to the schedule of assessments.

- All laboratory reports should be reviewed, signed and dated by Investigators. Any clinically significant changes will be recorded as AEs.
- Any single laboratory abnormality without clinical signs or symptoms needs to be repeated before qualifying as an AE.
- All clinically relevant abnormal laboratory tests occurring during the study may be repeated at appropriate intervals until they return to baseline or to a level deemed acceptable by the Investigator or until the abnormality is explained by an appropriate diagnosis.

Full details relating to the methodology of analysis, sample processing, labelling, storage, shipment and destruction procedures will be documented in a laboratory manual.

Test category	Test name	Time of assessment	Approx. mL
			per cycle
			(central assessment
			omy)
Phase 1 and 2 (unl	ess otherwise specified)	I	
Hematology	
 
Hematocrit (HCT), Hemoglobin (Hgb), Reticulocytes, red blood cell count (RBCC), mean cell hemoglobin (MCH), mean hemoglobin concentration (MCHC) and mean cell volume (MCV)
 
Platelets
 
White blood cells with Differential (Basophils, Eosinophils, Lymphocytes, Monocytes, Neutrophils)
 
	
 
Screening a,
 
C 1 b: D1 pre-dose, D2 c, D8, D15
 
C 2 b: D1 pre-dose, D8, D15
 
C 3 b: D1 pre-dose, D8
 
From Cycle 4 b: Day 1 pre-dose (CxD1)
 
EOT
 
	2 mL/sample 2 mL = Screening 8 mL = C1 6 mL = C2 4 mL = C3 2 mL = C4 -EOT
	• HbA1c	
 
Screening a
 
Every 12 weeks: pre-dose (C5D1 etc.).
 
EOT d
 
	
Clinical chemistry	
 
Alkaline phosphatase (ALP), alanine aminotransferase (ALT), aspartate-aminotransferase (AST), γ-glutamyltransferase (GGT), Total Bilirubin (also measure direct and indirect bilirubin if total bilirubin is >Grade 1), LDH, total CK, CK-MB
 
High sensitivity CRP (hsCRP)
 
Amylase, Lipase,
 
Total protein, Albumin
 
Bicarbonate, Calcium, Chloride, Sodium, Potassium Inorganic Phosphate, Magnesium, Ferritin,
 
Iron
 
Glucose, Cholesterol, Triglycerides, HDL, LDL
 
	
 
Screening a
 
C1-2b: D1 pre-dose, D8, D15
 
C 3b: D1 pre-dose, D8
 
From Cycle 4b: Day 1 pre-dose (CxD1)
 
EOT
 
	3.5 mL/sample 3.5 mL = Screening 10.5 mL = C1, C2 7 mL = C3 3.5 mL = C4 -EOT
	Creatinine, Blood Urea Nitrogen     (BUN) or Urea	0	
	
 
Fasting lipid profile, Glucose, Cholesterol, Triglycerides, HDL, LDL
 
Creat Clear (Est)
 
	Screening "	

 Table 6-8:
 Local/Central Clinical Laboratory Parameters Collection Plan

Test category	Test name	Time of assessment	Approx. mL
1 cor curegory			per cycle
			(central assessment only)
Coagulation	
 
Prothrombin time (PT) or INR,
 
Activated partial thrombonlastin
 
	
 
Screening a
 
Every cycle on Day 1b
 
	4.5 mL/sample:
	time (aPTT)	pre-dose (CxD1)	4.5 mL
	Thrombin time	• EOT	per visit
	• Fibrinogen		
	• D-Dimer		
Cardiac markers	Serum Troponin I	At screening a and when clinically indicated	3.5 mL/sample:
	
 
N-terminal pro B-type natriuretic peptide (NT-pro-BNP) (only for patients with previous cardiac history or when clinically indicated)
 
	At screening a (for patients with cardiac history only) and when clinically indicated	2 mL/sample
Thyroid	• Free T4	• Screening a	3.5 mL/sample:
	• TSH (Thyroid Stimulation	• Every 3 cycles pre-dose	
	Hormone)	(C3D1, C6D1, C9D1 etc.)	3.5 mL
		• EOI	per visit
Serological exam: Tumor	PSA, CEA, CA125, AFP, neuro specific enolase (NSE), CA15-3.	Screening a	5 mL/sample:
markers e	CA19-9, serum mesothelin	• Every cycle on Day 1 pre-dose (CxD1)	5 mL per visit
	(SMRP)Thyroglobulin, Calcitonin, Chromogranin A, human	• EOT	per visit
	choriogonadotropin		
Serology exam:	Anti-DNA antibodies (abs)	Screening a	18 mL/sample:
Auto-antibodies	• Anti-nuclear abs (ANA)	• Every 2 cycles pre-dose	
	Anti Cardiolip. IgG, IgM	C4D1, C6D1)	18.0 mL
	Anti Cardiolip. IgA (USA only)     Every 12 weeks ther		per visit
	Beta2-Glycoprotein I IgG, IgM     Dertial thromhon lastin time. Lynus	for 48 months of treatment	(Rheumatoid factor is
	anticoagulant (PTT-LA) Screen with Hexagonal Phase Confirm. As reflex (USA only)	• EOT	part of chemistry sample)
	• Lupus-Anticoagulant and Lupus sens. PTT-LA (EU and APAC only)		
	• Anti-mitochondrial abs (AMA; and AMA titer)		
	• Rheumatoid factor (RF)		
	• Acetyl-choline receptor antibodies (AChR)		
	
 
Anti-La (Anti-SSB), Anti-Ro (anti-SSA), Anti-Sm-Ab (anti-Smith) (new SmDP assay), anti U1RNP antibodies, anti-Jo-1 (anti-histidyl-tRNA synthetase), Scl-70 (topoisomerase) Ab (only if ANA 1:80 is positive)
 
		

Test category	Test name	Time of assessment	Approx. mL per cycle (central assessment only)
Virology	
 
Serology
 
(HBeAg, Anti-Hbe, HBcAb, HBsAb, HBsAg, HCV Ab, HIV-1/2 Ab)
 
	Screening a	3.5 mL/sample
	• (HIV-Ab, HBV DNA and HCV RNA)	

Screening a (if required)

CxD1 pre-dose

	8.5 mL/sample 8.5 mL per visit
Pregnancy	
 
Serum samples only for women of childbearing potential at screening (β-HCG)
 
	• Screening a	Part of the clinical chemistry sample
Urinalysis	
 
Bilirubin, Blood (hemoglobin), Glucose, Ketones, pH, Protein, Specific Gravity, White Blood Cells (Leucocyte Esterase)
 
Microscopy f(WBC, RBC; Hyaline Casts, Granular Casts, Waxy Casts, WBC Casts. RBC Casts, Epithelial Cells, Crystals, Mucous Threads, Bacteria, Yeast)
 
Urine dipstick pregnancy test (β-HCG) (not at Screening)
 
	
 
Screening a
 
Every cycle pre-dose (CxD1)
 
EOT
 
	

a In exceptional circumstances, the use of local labs for screening values may be considered.

*b* Parameters are also assessed at local laboratories.

c In Phase 2, no sample will be taken at C1D2.

*d* Only if the previous assessment has not been performed within the last 3 months.

e To be performed in Central laboratory only, where applicable.

f Only if clinically indicated.

#### 6.5.7 Vital Signs

Vital signs, including heart rate (HR), blood pressure (BP), respiratory rate, and temperature will be assessed at the screening visit and periodically during the treatment period as described in the Schedule of Assessments.

Heart rate and BP need to be established as a standard assessment (after 5 minutes in the supine position and after 5 minutes standing) during screening only. For all other visits supine position will be used.

During Cycles 1 and 2, BP and HR will be monitored in the clinic every 15 minutes during the infusions of study treatment and every 30 minutes in between the infusions (for combination therapy) and after the last infusion of study treatment for 1 hour and, during Phase 1, before the patients are discharged from the hospital on C1D2. In Phase 1, if the patient does not stay in the clinic for 24 hours on C1D1 (and instead may be released into after hour care per institutional standard), BP and HR need also to be monitored at 6 to 8 hours after the last infusion and/or before the patient is discharged into after hour care. This schedule maybe altered depending on emerging data.

Any changes from baseline in BPs and HR findings judged to be clinically significant by the Investigator will be recorded as AEs. In such cases, vital signs will be repeated at appropriate intervals until they return to baseline or to a level deemed acceptable by the Investigator or until the abnormality can be explained by an appropriate diagnosis.

#### 6.5.8 12-lead ECG

At the timepoints indicated in Table 6-9, a triplicate 12-lead ECG will be performed at screening and in accordance with PK measurements (the ECG should be recorded as close as possible to the timepoint, when the PK sample is drawn). At each timepoint three ECG recordings should be taken one after another.

Before the ECG, the patient should be supine for at least 10 minutes. All ECGs should be recorded with the patient in the same physical position. ECG traces are to be reviewed by a qualified physician at the study site (physician to sign, date and record interpretation on ECG trace). The Investigator will enter a signed and dated clinical interpretation of the ECG trace in the eCRF.

Any clinically significant abnormalities will be recorded as an AE. In such cases, triplicate ECGs will be repeated at appropriate intervals until they return to baseline or to a level deemed acceptable by the Investigator, or until the abnormality can be explained by an appropriate diagnosis.

Cycle	Day	Time a
Screening	-28 to -1	Twice b
1	1	Pre-infusion
1	1	1.5 hours (±5 min) post-infusion start
3	1	Pre-infusion
3	1	1.5 hours (±5 min) post-infusion start
6	1	Pre-infusion
6	1	1.5 hours (±5 min) post-infusion start
EOT	-	Anytime
Unscheduled c	-	Anytime

 Table 6-9:
 12-lead ECG Collection Plan for Phase 1 and 2

ECG=electrocardiogram; EOT=end of treatment.

a All ECGs will be performed in triplicates

b ECGs will be taken twice during the screening period, at least 3 days apart

c In case an ECG is performed due to an unexpected cardiac signal then an additional PK sample should be collected at the same time

The Investigator or designated physician will review the ECGs and may refer to a local cardiologist if appropriate. All ECG data will also be collected digitally and will potentially be transferred electronically as described in the ECG manual for central analysis of QTc data.

If an abnormal ECG finding at screening is considered by the Investigator to be clinically significant, it should be reported as a concurrent condition. During the study, clinically significant abnormal ECG findings not present at screening should be reported as an AE.

Troponin I and additionally other cardiac markers, ie, CK, CK-MB, BNP (only for patients with a history of cardiac disease), AST and lactate dehydrogenase (LDH) depending on the Investigators decision and if clinically indicated should also be assessed on identification of abnormal ECG findings, eg, new repolarization abnormalities, found to be possibly clinically significant by Investigators judgement. A repeat cardiac marker assessment should also be performed 24 hours later. The same Troponin isoform I should be assessed at each of the visits.

### 6.5.9 Virology Tests

Blood samples for HIV and hepatitis virology tests will be taken at screening. For those who have seropositivity of any markers indicating current or previous HBV (any seropositivity of HB s-Antigen, HB s-Antibody, HB c-Antibody, HB e-Antigen or HB e-Antibody, and/or detectability of HBV DNA) and/or HCV infection (seropositivity of HCV antibody and/or detectability of HCV RNA), relevant virology tests (ie, serum HBV DNA load for HBV infected patients and/or serum HCV RNA load for HCV infected patients) will be repeated pre-dose of every cycle, additionally, as clinically indicated (eg, a 2 to 3xULN rise in ALT).

Active HBV infection is defined as HBV viral load  $\geq 2000 \text{ IU/mL}$  (10^4 copies/mL). Active HCV infection is defined as anti-HCV positive and detectable HCV RNA.

#### Methods of assessment

For patients seropositive in HBV and/or HCV, virus replication status will be assessed by serum HBV DNA and/or HCV RNA in International units per milliliter (IU/mL) over time.

#### Derivation or calculation of outcome variable

For HBV/HCV seropositive patients, changes in virus replication will be measured by changes from baseline in HBV DNA level or in HCV mRNA levels on log scale, and HBV DNA/HCV mRNA status will be further categorized into detectable and undetectable.

#### 6.5.10 Monitoring for Drug Induced Liver Damage

Patients will be monitored for clinical signs of liver impairment according to the FDA guidelines for drug induced liver injury (DILI) (55). The levels of acceptable AST and ALT values must be adapted accordingly for patients with liver metastases or HCC. Re-challenge of patients who developed DILI will be carefully explored by assessing the benefit/risk situation for each individual patient by the Safety Review Committee, taking the FDA guidelines into consideration.

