# **1.6.2** Possible Immune-related Toxicities Identified with Other ICIs

The manipulation of the immune response via checkpoint inhibition is associated with a unique spectrum of side effects termed immune-related adverse events (irAEs) or, occasionally, adverse events of special interest (AESI). IrAEs include dermatologic, gastrointestinal (GI), hepatic, endocrine, and other less common inflammatory events. IrAEs are believed to arise from general immunologic enhancement, and temporary immunosuppression with corticosteroids, TNF $\alpha$  antagonists, hormone replacement or other agents can be an effective treatment in most cases. These irAEs might also be expected after treatment with KY1044.

In general, treatment of moderate or severe irAEs requires interruption of the checkpoint inhibitor and the use of corticosteroid immunosuppression. Treatment is based upon the severity of the observed toxicity:

- For patients with Grade 2 (moderate) immune-related toxicities, treatment with the checkpoint inhibitor should be withheld and should not be resumed until symptoms or toxicity is Grade 1 or less. Corticosteroids (prednisone 0.5 mg/kg/day or equivalent) should be started immediately if applicable.
- For patients experiencing Grade 3 or 4 (severe or life-threatening) immune-related toxicities, treatment with the checkpoint inhibitor should be permanently discontinued. High doses of corticosteroids (prednisone 1 to 2 mg/kg/day or equivalent) should be given. When symptoms subside to Grade 1 or less, steroids can be gradually tapered over at least 1 month.

Serologic, immunologic and histologic (biopsy) data should be used to support an irAE diagnosis. Appropriate efforts should be made to rule out neoplastic, infectious, metabolic, toxin, or other etiologic causes of the irAE.

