# 5.6 Dose Modifications and Management of Toxicities

#### 5.6.1 Dose Modifications and Dose Delays

For patients who do not tolerate the protocol -specified dosing schedule, dose adjustments are permitted to allow the patient to continue the study treatment. The following guidelines must be followed:

- If a patient experiences an AE meeting the criteria for a DLT as outlined in Section 5.5 (including events occurring after Cycle 1), treatment should be withheld. Dose modifications for toxicities related to the study medication are summarized in Table 5-5. Following resolution of the toxicity to Grade 1 or to the patient's baseline value (as outlined in the safety management guidelines in Table 5-5), the patient may resume study treatment at the same or the next lower dose level (Table 5-2, Table 5-3) assessed to be safe (on the same dosing schedule [administration every 21 days]), if there is no evidence of disease progression as per iRECIST.
- For patients in the dose escalation part of the study receiving KY1044 in combination with atezolizumab, the KY1044 dose level will be lowered to the next lower dose level. **Dose reductions of atezolizumab are not allowed.**
- The decision to resume treatment with KY1044 as single agent or in combination with atezolizumab following the occurrence of a DLT is at the discretion of the Investigator. If the Investigator considers it to be in the patient's best interest to resume therapy before the toxicity has resolved to Grade 1, or to resume without dose reduction, this may be permitted on a case by case basis, following discussion with the Medical Monitor.
- Dose reductions for KY1044 to below 0.24 mg (less than starting dose -1) are not permitted.
- If a patient who misses more than one consecutive dose due to study treatment -related toxicity experiences clinical benefit, and in the opinion of the Investigator it is in the patient's best interest to remain on study, then the patient may continue treatment after discussion with the Medical Monitor.

- Patients who discontinue study treatment for a study related AE or a study -related abnormal laboratory value must complete their EOT visit and safety followup procedures as described in Section 5.6.2 below and be followed up for PFS and survival (please refer to Section 8.2.2).

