НЕРАТ	TIC				
Hepatit	Hepatitis				
Grade	CTCAE description	Management	Specialist referral		
1	AST, ALT >ULN-3xULN; total bilirubin >ULN- 1.5xULN	
 
Continue ICI
 
CMP or hepatic function panel once weekly
 
If liver enzyme and function tests are stable, reduce frequency of blood tests
 
			
2	AST, ALT >3-≤5xULN; total bilirubin >1.5-≤3xULN	
 
Hold ICI
 
Rule out viral hepatitis, autoimmune disease, biliary obstruction, new metastasis or thrombosis
 
Start prednisone 0.5-1 mg/kg/day (or equivalent dose of methylprednisolone) with 4-week taper
 
Monitor CMP twice a week
 
Liver biopsy is optional
 
Resume ICI when corticosteroid taper to 10 mg/day (toxicity Grade ≤1)
 
			
3 and 4	AST, ALT >5xULN; total bilirubin >3xULN	
 
Permanently discontinue ICI
 
Monitor CMP every 1–2 days
 
Start prednisone 1–2 mg/kg/day 
 
If refractory after 3 days, consider mycophenolate
 
 
 
If liver enzymes improve, taper corticosteroid over 4 weeks
 
Consider liver biopsy
 
 a is due to the indirect (non-conjugated) component only, and hemolysis as the etiology has been ruled of the indirect (non-conjugated) component only.	out as per institutional		
guidelin	guidelines (eg, review of peripheral blood smear and haptoglobin determination), then reduce one dose level and continue treatment at the discretion of the Investigator.				

Property of the Sanofi Group - strictly confidential

PAGE 71 OF 217
Amended Clinical Trial Protocol 07 KY1044/SAR445256-KY1044-CT01/TCD17370 - alomfilimab 10-Nov-2021 Version number: 1

Asymptomatic amylase and/or lipase elevation			
3 4	>2.0-5.0xULN >5.0xULN	Any study treatment-related Grade $\geq 3$ isolated amylase or lipase abnormality that is not associated with symptoms or clinical manifestations of pancreatitis does not require dose delay or discontinuation. The Kymab Medical representative should be consulted for such amylase or lipase abnormalities.	
Note: A and/or li	CT scan or other imaging study to pase. If asymptomatic Grade 2 ele	assess the pancreas, liver, and gallbladder must be performed within 1 week of the first occurrence of any vations of lipase and/or amylase occur again at the reduced dose, patients will be discontinued permanently	$r \geq$ Grade 3 of amylase from study treatment.
CARDI	AC		
Grade	CTCAE description	Management	Specialist referral

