1	Asymptomatic; clinical or diagnostic observations only	
 
Continue ICI
 
Ophthalmology referral within 1 week
 
Start lubrication drops (artificial tears)
 
	✓
2	Anterior uveitis; medical intervention indicated	
 
Hold ICI
 
Ophthalmology referral within 2 days, prior to initiating uveitis treatment
 
Coordinate treatment with ophthalmologist (eg, topical corticosteroids, cycloplegic agents, systemic corticosteroids)
 
	✓
3	Posterior or pan-uveitis (Note)	
 
Permanently discontinue ICI
 
In carefully selected cases it may be appropriate to restart treatment, cautiously, depending on severity, systemic response to immunotherapy and ocular response to topical, local or systemic prednisone (prescribed in coordination with ophthalmologist)
 
URGENT ophthalmology referral (preferably uveitis specialist) prior to initiating treatment. Co-ordinate treatment with specialists
 
Consider systemic corticosteroids in addition to intravitreal/periocular corticosteroids/topical corticosteroid treatment as recommended by ophthalmologist
 
	✓ URGENT
4	Blindness (20/200 or worse) in the affected eye	
 
Permanently discontinue ICI
 
URGENT ophthalmology referral (preferably uveitis specialist) prior to initiating any treatment. Co-ordinate treatment with specialists
 
Consider systemic corticosteroids in addition to intravitreal/periocular corticosteroids/topical corticosteroid treatment as recommended by ophthalmologist
 
	✓ URGENT

Amended Clinical Trial Protocol 07 KY1044/SAR445256-KY1044-CT01/TCD17370 - alomfilimab

Episcleritis (CTCAE scleral disorder)			
Grade	CTCAE description	Management	Specialist referral?
1	Asymptomatic; clinical or diagnostic observations only	
 
Continue ICI
 
Ophthalmology referral within 1 week
 
Start lubrication drops (artificial tears)
 
	J
2	Symptomatic, limiting instrumental ADL; moderate decrease in visual acuity (20/40 or better)	
 
Hold ICI
 
Ophthalmology referral within 2 days, prior to initiating uveitis treatment
 
Coordinate treatment with ophthalmologist (topical steroids, cycloplegic agents, systemic steroids) (See Note)
 
	1

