#### Amended Clinical Trial Protocol 07 KY1044/SAR445256-KY1044-CT01/TCD17370 - alomfilimab

10-Nov-2021 Version number: 1

		• Day 2-3 of corticosteroids/supportive care: If symptoms improve to $\leq$ Grade 2, start slow steroid tare: over $\geq$ 1 month. If symptoms do not improve, or worsen, treat as Grade 3-4	
		
 
Consider drug re-challenge if symptoms and imaging abnormalities resolve
 
	
		consider drug te endnenge it symptoms and imaging abnormanies resolve	
3	Severe symptoms; limiting	Permanently discontinue ICI	1
	indicated ADL; oxygen	Hospitalize; consider ICU care	
4	Life-threatening respiratory	• Pulmonary consultation for bronchoscopy with bronchoalveolar lavage. Consider biopsies for	$\checkmark$ (pulmonary and
	compromise; urgent	atypical lesions	infectious disease)
	intervention indicated (eg, intubation)	• Initiate methylprednisolone IV, 2 mg/kg/day	
	,	• Day 2-3 of corticosteroids/supportive care:	
		
 
If no clinical improvement, add infliximab or cyclophosphamide, mycophenolate mofetil or IVIG
 
	
		• If clinical improvement: reduce corticosteroids to 1 mg/kg/day and slowly taper over >2 months.	
		• Drug re-challenge:	
		• Grade 3: Consider drug re-challenge on a case-by-case basis after discussions weighing benefit/risk with the patient and only if symptoms and imaging abnormalities resolve	
		• Grade 4: Permanently discontinue ICI	
Notes:			
1. Cons	ider prophylactic antibiotics for P	CP for patients receiving at least 20 mg methylprednisolone or equivalent for $\geq$ 4 weeks	
2. Cons	ider calcium and vitamin D supple	mentation with prolonged steroid use	
3. All p	atients with Grade 2-4 pneumoniti	s receiving steroids should also be on proton pump inhibitor therapy for GI prophylaxis	
4. T-sp	ot testing should be undertaken to	exclude tuberculosis in any patient being considered for anti-TNF therapy, prior to starting anti-TNF treatm	nent.
Sarcoidosis			
Grade	CTCAE description	Management	Specialist referral?
1	Not defined in CTCAE	Consider holding ICI	1
		Close follow-up	
≥2		Consider corticosteroids	1
		Hold ICI	
	•		•

Property of the Sanofi Group - strictly confidential

Amended Clinical Trial Protocol 07	
KY1044/SAR445256-KY1044-CT01/TCD17370 - alomfilimab	

10-Nov-2021 Version number: 1

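### Re-challenge after drug-induced liver injury is assigned to the Safety Review Committee in Section 6.5.10, but Section 5.6.1 and the Table 5-5 hepatitis rows allow or bar resumption without reference to that review

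*Protocol*

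**What the plan says.** Four places in the protocol bear on whether a patient with treatment-related liver injury may be dosed again.

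- **Section 6.5.10.** "Re-challenge of patients who developed DILI will be carefully explored by assessing the benefit/risk situation for each individual patient by the Safety Review Committee". The sentence adds that FDA guidance is to be taken into account. It states no grade or laboratory limit. The section also says acceptable AST and ALT levels must be adapted for patients with liver metastases or HCC.
- **Table 5-5, hepatitis rows.** The table is limited to treatment-related toxicity. In the Grade 2 row treatment is held, then: "Resume ICI when corticosteroid taper to 10 mg/day", once toxicity is Grade 1 or less. In the Grade 3 and 4 row, the band is "AST, ALT >5xULN; total bilirubin >3xULN" and the action is "Permanently discontinue ICI".
- **Section 1.6.2.** "For patients experiencing Grade 3 or 4 (severe or life-threatening) immune-related toxicities, treatment with the checkpoint inhibitor should be permanently discontinued".
- **Section 5.6.1.** It opens its list with "The following guidelines must be followed". Treatment is withheld for an event meeting the DLT criteria, including after Cycle 1, and may resume on resolution. The decision to resume is the Investigator's. Discussion with the Medical Monitor is required for resuming before Grade 1, for resuming without a dose reduction, and for continuing after more than one consecutive missed dose.

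Table 5-4 brings the liver into 5.6.1: total bilirubin of Grade 2 or higher together with ALT/AST of Grade 2 or higher is a DLT criterion.

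**The concern.** The SRC's role in 6.5.10 appears in a monitoring section. The rules a site consults during an event, 5.6.1 and Table 5-5, name other decision-makers or none. Neither points to 6.5.10, and 6.5.10 points to neither.

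At stake is re-exposure after combined transaminase and bilirubin elevation in a first-in-human study that, under Section 3.3, has no independent data monitoring board. A site could follow 5.6.1 and the Grade 2 hepatitis row to the letter and omit the individual assessment 6.5.10 calls for. At Grade 3-4 the question is whether permanent discontinuation is final or whether the SRC may reopen it.

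**Working it through.** The plan gives no figure to reproduce, so the check sets the rules side by side on three illustrative patients. Assumptions: each event is treatment-related with no other cause, and raised ALT/AST with raised bilirubin counts as DILI. Bands are those of Table 5-5: Grade 2 is ALT/AST above 3 to 5 x ULN and bilirubin above 1.5 to 3 x ULN; Grade 3-4 is anything higher.

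| Patient | Table 5-5 and 1.6.2 | 5.6.1 | 6.5.10 |
|---|---|---|---|
| A: ALT 4 x, bilirubin 2.5 x ULN (both Grade 2; Table 5-4 DLT criterion) | Hold; resume on steroid taper at Grade 1 or less | Investigator decides; Medical Monitor in three situations | SRC assesses re-challenge |
| B: ALT 6 x, bilirubin 2.5 x ULN (ALT in the Grade 3-4 band) | Permanent discontinuation | Investigator decides, with a reference to Table 5-5 | SRC assesses re-challenge, no stated grade limit |
| C: ALT 6 x ULN, normal bilirubin | Permanent discontinuation | As Table 5-5 if treated as hepatitis | Applies only if the event is judged DILI |

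**Patient A.** Table 5-5 and 5.6.1 agree on holding and on resumption after recovery. The SRC step is the whole difference. It is missing under 5.6.1 and, independently, under the Grade 2 row, so the gap does not depend on the event being a formal Cycle 1 DLT.

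**Patient B.** The hepatitis row has no re-challenge line. Other rows that discontinue permanently do write one in. Grade 3 uveitis: "In carefully selected cases it may be appropriate to restart treatment, cautiously, depending on severity". Grade 3 pneumonitis: "Grade 3: Consider drug re-challenge on a case-by-case basis after discussions weighing benefit/risk with the patient". The silence of the hepatitis row therefore reads as no exception. The note beneath it has lost its opening words in the text available here; what remains concerns bilirubin raised only through the indirect component, and nothing is rested on it.

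**Do other provisions supply the step?** Sections 3.3 and 5.5 have the SRC review safety data on an ongoing basis, which is not a check before one patient resumes. Section 7.1.6 and Appendix 3 make ALT/AST elevation with raised bilirubin or jaundice reportable within 24 hours in atezolizumab-treated patients. Reporting is not approval to resume, and that rule does not reach single-agent patients.

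**Size.** Section 1.6.4 gives immune-related hepatitis of any grade in 9.0% of 2616 patients on atezolizumab monotherapy: 0.090 x 2616 = 235.4. If that rate carried over to the maximum enrolment of 412, the count would be 0.090 x 412 = 37.1. This is context only: it covers all grades, comes from a different treatment, and does not give the share with the combined pattern.

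**The case against.** The best defence is that the passages can be read together. Section 5.6.1 is general and permissive, while 6.5.10 is specific, so a careful site can comply with both by obtaining SRC review before using the Investigator's discretion. Section 5.6.1 ties resumption to Table 5-5, and Section 5.6.2 describes the evaluations in that table as recommended. Permanent discontinuation as the default with a committee route above it would be coherent. The SRC includes, at a minimum, the Principal Investigators or designees and the Sponsor's physicians, so the people applying Table 5-5 are not strangers to 6.5.10.

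Much of this stands. The documents permit the harmonised reading; they do not state it. Section 5.6.1 presents its guidelines as mandatory, and a site working from it is never sent to 6.5.10.

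Three stronger inferences fail:

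- A reader might infer that the Investigator acts alone. Section 5.6.1 requires Medical Monitor discussion in three situations, Section 5.3 makes permanent discontinuation the default after more than one consecutive dose skipped for related toxicity, and Section 8 lets the Medical Monitor's opinion support stopping.
- A reader might infer that 6.5.10 authorises re-challenge after Grade 3-4 hepatitis without limit. It provides for an assessment, not an approval, and the FDA guidance it cites may contain limits that cannot be assessed here.
- A reader might infer that isolated ALT/AST elevation lies outside DILI. Section 6.5.10 gives no definition that excludes it.

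**Conclusion.** The point holds as a conflict between written safety rules. Section 6.5.10 calls for individual SRC assessment before re-challenge after DILI. Section 5.6.1 and the Grade 2 hepatitis row allow resumption after the combined liver pattern without it. At Grade 3-4, Table 5-5 and 1.6.2 discontinue permanently with no stated exception, while 6.5.10 has no grade limit in its own words.

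The conclusion rests on treating raised ALT/AST with raised bilirubin as DILI, as Appendix 3 does for potential cases. The number affected should be small but cannot be derived from the documents. The ORR analysis, sample size and error rates are untouched. It is worth correcting because it concerns who authorises re-exposure after liver injury and the correction is cheap. Separately, and only clerically, Appendix 3 refers to 6.5.10 for the definition of Hy's law, which 6.5.10 does not contain.

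**What to change.** In Section 5.6.1 and the Table 5-5 hepatitis rows, cross-refer to 6.5.10 and state two rules.

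(a) For a treatment-related event meeting the combined bilirubin and ALT/AST criterion of Table 5-4, or raised ALT/AST with clinical jaundice, held treatment is not resumed without documented SRC review. This covers single-agent and combination patients. The discretion of the Investigator and Medical Monitor in 5.6.1 does not replace the review. The 6.5.10 adaptation for liver metastases or HCC applies; it is needed because Section 4.3 admits patients with liver involvement at ALT or AST up to 5 x ULN.

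(b) Treatment-related Grade 3-4 hepatitis, with or without raised bilirubin, stays permanently discontinued under Table 5-5 and 1.6.2. The SRC route in 6.5.10 applies only below that level.

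Rule (b) matters for consistency. If the SRC route stayed open for Grade 3-4 ALT/AST with raised bilirubin while isolated Grade 3-4 elevation was barred, the more severe pattern would be handled more leniently. Under both rules, patient A waits for SRC review, and patients B and C stop permanently.

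Add the Hy's law definition to 6.5.10 in the same amendment. The cost is protocol wording and a short delay for SRC review in a few patients.
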